7.1.5 Radiographic Response Criteria

All radiographic response criteria are as per PCWG3 criteria summarized below.

7.1.5.1 Nodal Disease

Up to five (5) lesions are recorded per site of disease. These will be assessed as per RECIST 1.1 with the following PCWG3 caveats:

1. Changes in size are recorded using a waterfall plot
2. Favorable change is confirmed with a second scan
3. Complete elimination of disease at any site is recorded separately

4. Only changes in lymph nodes that were ≥ 1.5 cm in the short axis are reported
5. Changes in pelvic (regional) nodes versus extrapelvic (distant/metastatic) nodes are recorded separately

7.1.5.2 Visceral Disease

Visceral disease includes lesions in lung, liver, adrenal, and CNS sites. These will be assessed as per RECIST 1.1 with the following PCWG3 caveats:

1. Changes in liver, lung, adrenal, and CNS sites are recorded separately.
2. Only changes in lesions ≥ 1.0 cm in the longest dimension are reported

7.1.5.3 Bone Disease

Bone disease is evaluated as per PCWG3 criteria, with changes recorded as improved or stable (no new lesions) or worse (new lesions). Additional PCWG3 caveats include:

1. Changes in intensity of uptake alone do not constitute progression or regression
2. No new lesions: continue therapy in absence of other signs of progression
3. New lesions (progression) is defined by the following per PCWG3:
 - a. Exclude pseudoprogression in the absence of symptoms or other signs of progression
 - b. At least two new lesions on first post-treatment scan, with at least two additional lesions on the next scan (2+2 rule)
 - c. If at least two additional new lesions are seen on the next (confirmatory) scan, the date of progression is the date of the first post-treatment scan, when the first two new lesions were documented
 - d. For scans after the first post-treatment scan, at least two new lesions relative to the first post-treatment scan confirmed on a subsequent scan

7.2 Antitumor Effect- Non-Prostate Malignancies

(For Cohort B only)

For patients with metastatic non-prostate cancer and measurable disease, response and progression will be evaluated using the new international criteria proposed by the Response Evaluation Criteria in Solid Tumors (RECIST) Committee [34]. Changes in only the largest diameter (unidimensional measurement) of the tumor lesions are used in the RECIST v1.1 criteria.

Immunotherapy drugs such as nivolumab and ipilimumab can initially cause inflammation in the early stages of treatment. Immune-related RECIST (irRECIST) utilizes RECISTv1.1 but considers an inflammatory response (or “pseudo-progression”) as normal. The main difference between RECISTv1.1 and irRECIST is that patients can stay on trial after the first progressive disease (PD) assessment (as per RECISTv1.1) if using immune-related

RECIST criteria. This PD per RECISTv1.1 is then re-labeled as immune related stable disease (irSD) per irRECIST and requires addition of unidimensional measurements of all new lesions (that meet the definition of target lesion) to be added to the sum of longest diameters (SLD) calculation for response assessment. Importantly, immune-related progression (irPD) must be confirmed by a follow-up scan at least 4 weeks (within 4-8 weeks) following the initial PD/irSD assessment in order to take the patient off the trial.

Subjects that are deemed to have clinical progression and unstable should not be continued on therapy after PD (per RECISTv1.1) and are therefore not required to have repeat tumor imaging for confirmation as per irPD definition. It is at the discretion of the site investigator whether to continue a subject on study treatment until repeat imaging is obtained. This clinical judgment decision by the site investigator should be based on the subject's overall clinical condition, including performance status, clinical symptoms, and laboratory data.

Treatment Beyond Progression

Accumulating evidence indicates a minority of subjects treated with immunotherapy may derive clinical benefit despite initial evidence of PD.

Subjects treated will be permitted to continue study treatment beyond initial RECISTv1.1 defined PD, assessed by the investigator, as long as they meet the following criteria:

- Investigator determined clinical benefit
- Tolerance of study drug
- Stable performance status
- Treatment beyond progression will not delay an imminent intervention to prevent serious complications of disease progression (e.g., CNS metastases)

A radiographic assessment/ scan should be performed within 4-8 weeks of initial investigator-assessed progression to determine whether there has been a decrease in the tumor size or continued PD (termed irPD).

The assessment of clinical benefit should be balanced by clinical judgment as to whether the subject is clinically deteriorating and unlikely to receive any benefit from continued treatment.

If the investigator feels that the subject continues to achieve clinical benefit by continuing treatment, the subject should remain on the trial and continue to receive monitoring according to the Study Calendar (see Section 6.1).

Immune-related Progressive Disease (irPD): For the subjects who continue study therapy beyond progression, further progression is defined as an additional 20% increase in tumor burden with a minimum 5 mm absolute increase from time of initial PD, unequivocal worsening of NT lesions, or appearance of new lesions since the last evaluation. This includes an increase in the sum of diameters of all target lesions and/ or the diameters of new measurable lesions compared to the time of initial PD. Study treatment should be discontinued permanently upon documentation of further progression (i.e. irPD).

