7.4 Response Criteria

7.4.1 Evaluation of Target Lesions

Prior to the first PD assessment, patients will be evaluated according the following RECISTv1.1 response:

Complete Response (CR): Disappearance of all target lesions, determined by two separate observations conducted not less than 4 weeks apart. There can be no appearance of new lesions.

Partial Response (PR): At least a 30% decrease in the sum of the longest diameter (LD) of target lesions, taking as reference the baseline sum LD. There can be no appearance of new lesions.

Progressive Disease (PD): At least a 20% increase in the sum of the LD of target lesions (with a minimum absolute increase of 5 mm), taking as reference the smallest sum LD recorded since the treatment started, or the appearance of one or more new lesions.

Stable Disease (SD): Neither sufficient shrinkage to qualify for PR (taking as reference the baseline sum LD) nor sufficient increase to qualify for PD (taking as reference the smallest sum LD since the treatment started).

For Cohort B only: After the first PD assessment per RECISTv1.1 (=irSD per irRECIST), patients will be evaluated for irPD at least 4 weeks apart according to the following definition:

Immune-related Progressive Disease (irPD): At least a 20% increase in the sum of the LD of target lesions (with a minimum absolute increase of

5 mm), taking as reference the smallest sum LD recorded since the treatment started, or appearance of new lesions since the last evaluation.

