7.4.3 Evaluation of Best Overall Response

The best overall response is the best response recorded from the start of the treatment until disease progression/recurrence (taking as reference for progressive disease the smallest measurements recorded since the treatment started). The patient's best response assignment will depend on the achievement of both measurement and confirmation criteria.

Evaluation as per RECISTv1.1 and irRECIST.

Target Lesions	Non-Target Lesions	New Lesions	Overall Response per RECIST 1.1	Overall Response per irRECIST (Cohort B only)	Best Response for this Category Also Requires:
CR	CR	No	CR	N/A	>4 wks. confirmation
CR	CR Non-CR/SD	No	PR	N/A	>4 wks. confirmation
PR	CR Non-CR/PD	No			
SD	CR Non-CR/PD	No	SD	N/A	documented at least once >4 wks. from baseline
PD	Any	Any	PD	irSD	>4 wks. from baseline;
Any	PD*	Any			
Any	Any	Yes			
PD	Any	Any	N/A	irPD	No further confirmation required
Any	PD*	Any			
Any	Any	Yes			

*In exceptional circumstances, unequivocal progression in non-target lesions may be accepted as disease progression.

Note: Patients with a global deterioration of health status requiring discontinuation of treatment without objective evidence of disease progression at that time should be reported as "*symptomatic deterioration*." Every effort should be made to document the objective progression even after discontinuation of treatment.

N/A=not applicable

Note: If subjects respond to treatment and are able to have their disease resected, the patient's response will be assessed prior to the surgery

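### Sections 7.2 and 7.4.1 measure Cohort B irPD from different reference scans, so the same confirmation scan can require permanent discontinuation under one and not the other

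*Combined protocol and SAP*

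**What the plan says.** Four places in the protocol bear on irPD in Cohort B.

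- **Section 7.2, general text.** The first RECIST 1.1 progression is relabelled irSD, and "immune-related progression (irPD) must be confirmed by a follow-up scan at least 4 weeks (within 4-8 weeks) following the initial PD/irSD assessment". The relabelling also "requires addition of unidimensional measurements of all new lesions" to the sum, if they are large enough to be target lesions.
- **Section 7.2, Treatment Beyond Progression.** The 4-8 week scan is done "to determine whether there has been a decrease in the tumor size or continued PD (termed irPD"). A later paragraph, headed irPD, covers patients who stay on treatment: "further progression is defined as an additional 20% increase in tumor burden with a minimum 5 mm absolute increase from time of initial PD". The reference to initial PD is then repeated for the sum including new measurable lesions. The consequence follows: "Study treatment should be discontinued permanently upon documentation of further progression (i.e. irPD").
- **Section 7.4.1, Cohort B only.** After the first RECIST 1.1 progression, "patients will be evaluated for irPD at least 4 weeks apart according to the following definition". That definition is a 20% increase with at least 5 mm, "taking as reference the smallest sum LD recorded since the treatment started, or appearance of new lesions since the last evaluation".
- **Section 7.4.3.** The response table prints no reference scan for irPD. Its irPD row uses target-lesion PD, which Section 7.4.1 defines against the smallest sum. The text above the table does the same for progression: "taking as reference for progressive disease the smallest measurements recorded since the treatment started".

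Section 5.4 ends treatment on progression as defined anywhere in Section 7.0, so it brings in both definitions. Section 11.3 lists duration of therapy among the Kaplan-Meier endpoints, reported by cohort.

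**The concern.** One label, irPD, is given to one group of patients with the same percentage and millimetre thresholds but two starting points. The scan at first progression is normally larger than the smallest sum, so the Section 7.2 threshold is the higher of the two. A patient whose disease has neither grown nor shrunk since first progression falls between them. That is the situation the confirmation scan is meant to resolve.

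Because irPD carries a permanent-discontinuation instruction, two sites that each follow the text could act oppositely on the same scan. Duration of therapy would then depend partly on which section a site had read.

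**Working it through.** The plan states no figure on this point, so there is nothing to reproduce. The check is to apply both size rules to the same scans. All lesion sums below are illustrative assumptions, because the documents give none.

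**Notation.** N is the smallest sum since treatment started. P is the sum at initial progression, including any new measurable lesion added under Sections 7.2 and 7.2.2. C is the confirmation sum.

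**Rules**
- Section 7.4.1: C ≥ max(1.2N, N + 5).
- Section 7.2, further-progression sentence: C ≥ max(1.2P, P + 5).

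The two classify a patient oppositely when C is at or above the first threshold and below the second. Since P ≥ N, the second threshold is never the lower one, so the split runs one way only: irPD by 7.4.1, not by 7.2.

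**General result for an unchanged sum (C = P).** If initial progression was met by size, then P ≥ max(1.2N, N + 5) and the 7.4.1 rule is met. P is always below max(1.2P, P + 5), so the 7.2 rule is not met. The split therefore occurs in every such case.

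**Worked cases (mm)**

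| Case | N | P | 7.4.1 threshold | 7.2 threshold | Opposite classification | Unchanged sum |
|---|---|---|---|---|---|---|
| Target growth | 80 | 100 | max(96, 85) = 96 | max(120, 105) = 120 | 96 to below 120 | split |
| New 12 mm lesion, P = 50 + 12 | 50 | 62 | max(60, 55) = 60 | max(74.4, 67) = 74.4 | 60 to below 74.4 | split |
| New 12 mm lesion, P = 80 + 12 | 80 | 92 | max(96, 85) = 96 | max(110.4, 97) = 110.4 | 96 to below 110.4 | meets neither |

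Relative to the initial-progression scan, the lower ends of the bands are 96/100 = −4.0%, 60/62 = −3.2% and 96/92 = +4.3%. Each upper end is just below +20%. In the first two cases the band includes no change and a slight decrease. The second shows that growth of the original target lesions is not needed, since 62/50 = +24% comes from the new lesion alone. The third marks the limit: 92/80 = +15% is short of 20%, so an unchanged sum meets neither size rule.

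**Scope.** Both definitions also count a new lesion since the last evaluation, and non-target worsening can establish irPD under Section 7.2 and the 7.4.3 table. The size conflict therefore decides the outcome only when neither is present.

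**The case against.** The strongest reply is that the rules are sequential. The Treatment Beyond Progression text runs in order: the 4-8 week scan, then continuation if the investigator sees benefit, then a definition of further progression for those who continue. The words about further and additional growth suit a later step, with Section 7.4.1 governing the confirmation scan. On that reading an unchanged sum is simply continued progression at confirmation, and Section 7.2 agrees with 7.4.1.

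This reading is available but is not stated. Section 7.2 ties irPD to the 4-8 week scan and gives the same label to the further-progression rule. Section 7.4.1 applies its definition from the first progression onward, with no end point. What stands is that Section 7.2 is not uniform within itself: its sentence on the scan calls continued progression irPD without asking for another 20%, and its definition does ask for it. That is a further reason to reconcile.

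A second reply is that Section 7.2 already leaves continuation partly to the investigator, so sites would differ under a single reference scan too. That is true, and the share due to the reference scan cannot be isolated. The discretion does not displace the instruction to stop permanently on irPD, which depends on what irPD means.

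A third reply is that the effect is small: a descriptive summary in a secondary cohort of 15, and possibly no patient in the band. That limit is accepted. The general result above shows when a split must occur, not how often it would.

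**Conclusion.** The concern holds. As written, Section 7.2's further-progression definition and Section 7.4.1 give different size thresholds for irPD in the same patients, and no text sets precedence or assigns them to different scans. After a first progression by size, an unchanged sum is always irPD by the 7.4.1 size rule and never by the 7.2 one. In the illustrative cases the band of opposite classification is 96 to below 120 mm, 60 to below 74.4 mm, or 96 to below 110.4 mm.

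This rests on assumed lesion sums and on a confirmation scan with no further new lesion and no non-target worsening. Those affected are the Cohort B patients who continue past first progression and whose sum falls in the band. The documents do not let that number be estimated.

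Treatment stopping is affected, and through it the duration-of-therapy estimate. The Cohort B response rate is assessed by RECIST 1.1, so it, the 3-of-15 rule and the 76% power stand. The inconsistency should be corrected, but it does not undermine the trial's decision rules.

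**What to change.** Reconcile Section 7.2 (both the sentence on the purpose of the 4-8 week scan and the irPD definition), Section 7.4.1 and the Section 7.4.3 table to one irPD definition with one stated reference scan, worded the same throughout. The wording should make clear how an unchanged sum at confirmation is classified. If a two-step sequence was intended, the text must say so and label the steps separately. Then check that Section 5.4 and the Section 7.2 provisions for clinically unstable patients after first progression remain consistent with it.

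This review does not say which reference scan or stopping rule is right. Because the wording fixes a treatment-stopping criterion, that choice is a clinical one for the sponsor. The cost is a change of protocol wording, with no new data or assessments.

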7.2.1 Definitions

Evaluable for toxicity. All patients will be evaluable for toxicity from the time of their first treatment with study drug.

Evaluable for objective response. All patients enrolled who received at least 1 cycle(s) of therapy, and who have measurable disease present at baseline and have had their disease re-evaluated will be considered evaluable for response. These patients will have their response classified according to the definitions stated below. (Note: Patients who exhibit objective or clinical disease progression prior to the end of cycle 1 will also be considered evaluable.)

7.2.2 Disease Parameters

Measurable disease. Measurable lesions are defined as those that can be accurately measured in at least one dimension (longest diameter in the plane of measurement is to be recorded) with a minimum size of:

- 10mm by CT scan (irrespective of scanner type) for studies with a slice thickness of \leq 5mm or twice the slice thickness or MRI
- 10mm caliper measurement by clinical exam (lesions which cannot be accurately measured with calipers should be record as non-measurable)
- 20mm by chest X-ray (if clearly defined and surrounded by aerated lung)

All tumor measurements must be recorded in millimeters (or decimal fractions of centimeters).

Malignant lymph nodes: To be considered pathologically enlarged and measurable, a lymph node must be \geq 15mm in short axis when assessed by CT scan (CT scan slice thickness recommended to be no greater than 5 mm). At baseline and in follow-up, only the short axis will be measured and followed.

Note: Tumor lesions that are situated in a previously irradiated area will only be considered measurable if they have had subsequent progression by at least 5mm.

Non-measurable disease. All other lesions (or sites of disease), including small lesions (longest diameter $<$ 20 mm with conventional techniques or $<$ 10 mm using CT scan), are considered non-measurable disease. Bone lesions without measurable soft tissue component, leptomeningeal disease, ascites, pleural/pericardial effusions, lymphangitis cutis/pulmonis, inflammatory breast disease, abdominal masses (not followed by CT or MRI), and cystic lesions are all non-measurable.

Target lesions. All measurable lesions up to a maximum of 2 lesions per organ and 5 lesions in total should be identified as **target lesions** and recorded and measured at baseline. Target lesions should be selected on the basis of their size (non-nodal lesions with the longest diameter), be representative of all involved organ(s), but in addition should be those that lend themselves to reproducible repeated measurements. If a non-nodal lesion is either not present or is initially measured with longest diameter $<$ 10mm as a non-target then grows to $>$ 10mm after baseline, this lesion then becomes a new target lesion as per irRECIST criteria. The non-nodal longest diameter is then added to the sum of diameters, and patient response is calculated with the new lesion.

Lymph nodes merit special mention since they are normal anatomical structures which may be visible by imaging even if not involved by tumor. Pathological nodes which are defined as measurable and may be identified as target lesions must meet the criterion of a short axis of \geq 15mm by CT scan. Only the short axis of these nodes will contribute to the baseline sum. The short axis of the node is

the diameter normally used by radiologists to judge if a node is involved by solid tumor. Nodal size is normally reported as two dimensions in the plane in which the image is obtained (for CT scan this is almost always the axial plane; for MRI the plane of acquisition may be axial, sagittal or coronal). The smaller of these measures is the short axis. For example, an abdominal node which is reported as being 20mm x 30mm has a short axis of 20mm and qualifies as a malignant, measurable node. In this example, 20mm should be recorded as the node measurement. All other pathological nodes (those with short axis ≥ 10 mm but < 15 mm) should be considered non-target lesions. Nodes that have a short axis < 10 mm are considered non-pathological and should not be recorded or followed.

A sum of the diameters (longest for non-nodal lesions, short axis for nodal lesions) for all target lesions will be calculated and reported as the baseline sum diameters. If lymph nodes are to be included in the sum, then as noted above, only the short axis is added into the sum. The baseline sum diameters will be used as reference to further characterize any objective tumor regression in the measurable dimension of the disease. If a non-target lymph node grows to > 15 mm after baseline, this node then becomes a new target lesion as per irRECIST. The nodal short axis is then added to the sum of diameters, and patient response is calculated with the new lesion.

Non-target lesions. All other lesions (or sites of disease) including pathological lymph nodes should be identified as non-target lesions and should also be recorded at baseline. Measurements are not required and these lesions should be followed as 'present', 'absent', or in rare cases 'unequivocal progression' (more details to follow). In addition, it is possible to record multiple non-target lesions involving the same organ as a single item on the case record form (e.g. 'multiple enlarged pelvic lymph nodes' or 'multiple liver metastases').

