7.4.2 Evaluation of Non-Target Lesions

Complete Response (CR): Disappearance of all non-target lesions and normalization of tumor marker level. All lymph nodes should be non-pathological in size (<10 mm short axis).

Incomplete Response/Stable Disease (SD): Persistence of one or more non-target lesion(s) and/or maintenance of tumor marker level above the normal limits.

Progressive Disease (PD): Appearance of one or more new lesions and/or unequivocal progression of existing non-target lesions.

Although a clear progression on non-target lesions in absence of stable target lesions is exceptional, the opinion of the treating physician should prevail in such circumstances.

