11.0 STATISTICAL CONSIDERATIONS

11.1 Study Design/Study Endpoints

This is a multi-center, prospective, one arm, 3 cohort study to evaluate the efficacy of immunotherapy in patients with metastatic cancers and CDK12 loss. Patients with metastatic castration resistant prostate cancer (mCRPC) will be enrolled in Cohort A until 25 evaluable patients are identified. Once Cohort A is full, mCRPC patients will enroll in Cohort C. Patients with other metastatic subtypes will be enrolled in Cohort B.

An Mini-Max Simon Two-Stage design will be used to assess ORR defined as a 50% decline in PSA from baseline in CDK12 loss of function metastatic CRPC patients. It is assumed that an ORR of 30% or more would be interesting for further study compared to a reference ORR of 10% based on the KEYNOTE-199 trial [35]. Accrual of 25 objective PSA response evaluable patients will provide 80% power to detect this difference in ORR with a type I error of 5%. Interim analysis will be completed after 15 objective PSA response evaluable patients (Cohort A only). If 2 or more patients have a PSA response, then the 2nd stage will open and accrue 10 more patients. If 6 or more patients out of 25 have a PSA response, then the treatment will be recommended for further study in this population.

Cohort B will accrue 15 patients with non-prostate histology. A reference ORR of 5% is assumed in patients with non-prostate histology. With 15 patients, we have 76% power to detect an ORR of 25% with a one-sided type I error of 5%. If 3 or more responses are seen in cohort B then we will conclude that there is preliminary evidence of activity.

Cohort C will accrue 25 mCRPC patients. A reference ORR of 10% is assumed, allowing 80% power to detect an ORR of 30% or more with a one-sided type I error of 5%. If 6 or more patients out of 25 have a PSA response, then the treatment will be recommended for further study in this population.

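### Section 7.2.2 adds a growing non-target lesion to the target sum without requiring a first RECIST 1.1 PD; this conflicts with section 7.4 and could cost Cohort B responders

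*Combined protocol and SAP*

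**What the plan says.** Section 7.2.2 of the combined protocol and SAP defines target lesions for Cohort B. A non-nodal lesion that was absent, or was a non-target lesion under 10 mm, and later exceeds 10 mm is made a target lesion under irRECIST: "The non-nodal longest diameter is then added to the sum of diameters, and patient response is calculated with the new lesion". The nodal rule is parallel: "If a non-target lymph node grows to > 15 mm after baseline, this node then becomes a new target lesion as per irRECIST". The only timing in either rule is that the change comes after baseline.

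Section 7.4.1 opens with "Prior to the first PD assessment, patients will be evaluated according the following RECISTv1.1 response". It requires for CR and PR that "There can be no appearance of new lesions", and it makes any new lesion PD. Section 7.4.2 defines PD on non-target disease as "Appearance of one or more new lesions and/or unequivocal progression of existing non-target lesions". The table in 7.4.3 marks irRECIST as not applicable for CR, PR and SD.

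The introduction to section 7.2 says when irRECIST enlarges the sum: after a RECIST 1.1 PD has been relabelled irSD, the measurable new lesions are added. It does not mention existing non-target lesions that grow.

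The synopsis, section 2.5.1 and section 11.3 all score Cohort B response by RECIST 1.1. Section 11.1 sets the rule: "If 3 or more responses are seen in cohort B then we will conclude that there is preliminary evidence of activity".

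**The concern.** An assessor who follows 7.2.2 adds the lesion's full diameter to the follow-up sum, while the baseline sum contains none of it. A change of 1 or 2 mm across the size limit then looks like 11 to 16 mm of growth. An assessor who follows 7.4 leaves the target sum alone and asks only whether the non-target growth is unequivocal. The two can label the same scan differently, and no passage says which section prevails.

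At stake are the Cohort B response count, where one patient is 1/15 = 6.7 percentage points, and the radiographic progression date. That date feeds rPFS and the radiographic component of PFS (section 7.6) and duration of response (section 7.5). Because 7.4.3 counts best response only up to progression, a false early PD would also shut out a later PR.

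**Working it through.** **The plan's own figure.** Inputs from section 11.1: n = 15, reference rate 5%, target rate 25%, success at 3 or more responses. Exact binomial:
- P(X ≥ 3 | 15, 0.25) = 0.764, which matches the stated 76% power.
- P(X ≥ 3 | 15, 0.05) = 0.036, below the nominal one-sided 5%.

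These figures hold when response is scored by RECIST 1.1 alone.

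**Scan arithmetic.** Let B be the baseline target sum, N the smallest target sum so far, T the target sum at the scan, and L the diameter of the added lesion. Section 7.4 uses T; section 7.2.2 uses T + L. Thresholds from 7.4.1:
- PR if the sum is at least 30% below B.
- PD if it is at least 20% and at least 5 mm above N.

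The documents give no lesion sizes, so the sizes below are assumed. In each case the non-target growth is taken as not unequivocal.

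1. *Stable targets (T = N = B).* The change is L/B, so PD by the sum follows when B ≤ L/0.20.
   - Node 14 to 16 mm: 16/30 = +53%, 16/60 = +27%, 16/80 = +20%. PD for every B up to 80 mm; SD under 7.4.
   - Non-nodal lesion 9 to 11 mm: PD for every B up to 11/0.20 = 55 mm.

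2. *First follow-up scan, targets down 40% (T = 0.6B); PR under 7.4.* The change is −40% + L/B, so PR survives only if L/B ≤ 10%.
   - Node 16 mm: +13% at B = 30, −13% at B = 60, (60 + 16)/100 − 1 = −24% at B = 100. All three are SD. PR survives from B = 16/0.10 = 160 mm upwards.

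3. *Later scan, B = 100, N = T = 50, lesion grown from 8 to 12 mm.* Under 7.4 this is PR (−50%). Under 7.2.2 the sum is 62 mm, which is 12 mm and 24% above N: PD.

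L is positive, so at any one scan the addition moves the sum away from the PR threshold. It can remove a PR but cannot supply one.

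**Effect on the 3-of-15 rule.** 3/15 is 20.0% (exact 95% CI 4.3 to 48.1) and meets the rule; 2/15 is 13.3% (1.7 to 40.5) and does not. If a fraction m of true responders were lost, power would be P(X ≥ 3 | 15, 0.25(1 − m)):

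| m (assumed) | Power |
|---|---|
| 0 | 0.764 |
| 10% | 0.690 |
| 20% | 0.602 |
| 30% | 0.503 |
| 40% | 0.396 |

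**The case against.** The strongest defence is that 7.2.2 sits inside 7.2 and carries the irRECIST label, and that 7.2 places irRECIST additions after a first RECIST 1.1 PD. On that view 7.2.2 only says which lesions qualify, and the enlarged sum has its own use in deciding between irSD and irPD. Since the endpoint and analysis text name RECIST 1.1, a careful analyst would leave the response count alone.

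For brand-new lesions this stands. A reader might infer that a patient with a new 12 mm lesion and targets falling from 100 to 40 mm becomes a false responder, because the enlarged sum of 52 mm is 48% below baseline. The documents do not support that: 7.4.1 separately bars PR when a new lesion appears, the 7.4.3 table assigns PD, and best response stops at progression. The order is coherent: PD first, then irSD with the lesion added.

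For existing non-target lesions that grow, the defence fails. Such growth need not be a RECIST 1.1 PD, so the sequence in 7.2 may never start, and that sequence mentions only new lesions. The sole timing in 7.2.2 is after baseline.

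Two limits on size also stand. A PR confirmed before the lesion crosses the limit remains the best response. The endpoint is also secondary, with a conclusion of preliminary activity only.

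**Conclusion.** The point holds for existing non-target lesions that pass the size limit: as written, 7.2.2 conflicts with 7.4.1, 7.4.2 and the RECIST 1.1 definition of Cohort B response. Small growth can turn a PR into SD, or an SD or PR into PD.

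Two stronger readings go too far. A reader might infer that the 3-of-15 count does change. It could change, but scoring strictly by 7.4 and 11.3 leaves the count and the 76% power as stated. A reader might also infer that one scan can be PR, SD or PD. In each example a scan has two competing labels; all three appear only across different examples.

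The 80 mm and 160 mm limits rest on the assumed 16 mm node and, for the second, on a 40% shrinkage. The power range of 0.690 to 0.396 rests on assumed losses of 10 to 40% of responders. The true frequency is unknown. The correction is still worth making, because one patient can decide the Cohort B conclusion and the wording can be settled cheaply.

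**What to change.** In 7.2.2, limit both addition rules (non-nodal and nodal) to Cohort B irRECIST assessments made after the first RECIST 1.1 PD. State that lesions added this way never enter the RECIST 1.1 target sum, the Cohort B response count, or the RECIST 1.1 radiographic progression date used for rPFS and DOR. The same sentence aligns the wording for brand-new lesions with 7.2 and 7.4. Leave the PFS definition in 7.6 unchanged, since it also counts clinical progression.

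The cost is a wording amendment, with no new scans. Any Cohort B scan already scored with an added lesion should be re-read against 7.4. The target sum can be recomputed without that lesion, but whether the growth was unequivocal is a reader's judgement, and 7.2.2 does not require non-target measurements to be recorded.
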